We expect that FM patients will show reduced pleasantness of C-LTMR-optimal touch compared to healthy individuals as found in FM patients in [3] and LBP patients in [8]. We hypothesize that current depression and trauma history will be significant predictors of blunted C-LTMR touch pleasantness. Based on an effect size F^2 of 0.15, three predictors, alpha of 0.05, and power 0.8, this study will require $N = 77$ participants. We will round up to $N = 80$ and include $N = 40$ FM patients and $N = 40$ healthy controls. Based on effect sizes observed in [3] and [8], this sample size will also be sufficient for the comparisons of pleasant touch.

Furthermore, we expect that FM patients will show reduced analgesic benefit of pleasant touch compared to healthy controls, due to reduced touch pleasantness ratings and our theorized relationship between touch pleasantness perception and analgesia, and due to reduced endogenous pain modulation evidenced in the CPM paradigm. We expect reduced analgesic effects of touch pleasantness in FM due to altered pleasant touch perception in FM (and LBP) [3, 8]. The studies showing analgesic effects of affective touch showed effect sizes of approximately $d = 0.6$ [6] and $d > 2$ (for the large compression area) [7], respectively. We would need 24 participants to demonstrate the smaller effect size in each group (alpha of 0.05, power of 0.8). No previous study has examined how pleasant touch modulates pain in chronic pain compared to healthy adults. To observe a difference in affective pain modulation between patients and healthy controls, based on the average large effect size of 0.78 seen across studies in [27] for CPM, this study would require 27 participants in each group, so the 40 participants calculated for each group will be sufficient. The MRI portion of the study will be a pilot study ($N = 20$), intended to provide preliminary data for future grant applications.

Data Analyses and Interpretation

Scores on the depression and trauma history questionnaires will be used as linear regressors to predict ratings of gentle brushing pleasantness.

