10. HUMAN SUBJECTS

Subject Population

A total of 80 adults (40 patients with FM and 40 healthy volunteers), ages 18-65, will complete the behavioral portion of the study. We will match participants with FM and healthy control participants for age and sex at the group level. In addition, 20 adults (may be same or different individuals) will complete the pilot fMRI portion of the study. We will include all genders, races and ethnicities.

Inclusion Criteria:

All participants will be:

- 1) Between the ages of 18 and 65 years old
- 2) Fluent in English

Additional Inclusion Criteria for Chronic Pain Participants:

- 1) Reported diagnosis of Fibromyalgia (FM) by a physician, but no other chronic pain conditions of greater pain severity (diagnosis verified by medical records whenever possible)
- 2) Meets 2016 revised ACR diagnostic criteria (Wolfe, Clauw et al. 2016) for FM for more than 1 year (based on phone screen)

Additional Inclusion Criteria for Control Participants:

- 3) no indication of current pain or chronic pain (based on phone screen)

Exclusion Criteria:

- 1) Sensory, motor, or anatomic differences or injuries relevant to study procedures
- 2) Known anomalies of the central nervous system (including stroke, dementia, aneurysm, or personal history of psychosis)
- 3) Pregnancy
- 4) Inability to rate pain or sensations
- 5) Major medical conditions such as kidney, liver, cardiovascular (hypertension, preexisting cardiac arrhythmia), autonomic, pulmonary, or neurological problems (e.g., seizure disorder) or a chronic systemic disease (e.g., diabetes).
- 6) History of blood clots or clotting disorders
- 7) Current use of opiate medication(s)
- 8) Contraindications to MRI if participating in pilot MRI study
- 9) Unable to identify a heat stimulus 50C or lower that generates a rating of a 6 on our VAS scale
- 10) History of fainting or seizures
- 11) History of frostbite
- 12) Open cut or sore on hand to be immersed in cold water bath
- 13) Fracture of limb to be immersed
- 14) History of Reynaud's phenomenon (hands get white, then blue on exposure to cold, then red on warming)

We will recruit healthy controls (HC) that are group-matched to the chronic pain (FM) patients by age and sex.

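### N = 77 with power 0.8 belongs to the overall three-predictor F-test, not to the hypothesis that depression and trauma history are each significant predictors

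*Combined protocol and SAP*

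**What the plan says.** Section 9, Sample Size Determination & Power, states the Aim 1 hypothesis: "We hypothesize that current depression and trauma history will be significant predictors of blunted C-LTMR touch pleasantness". The next sentence gives the calculation, "Based on an effect size F^2 of 0.15, three predictors, alpha of 0.05, and power 0.8, this study will require" N = 77, and the plan continues: "We will round up to $N = 80$ and include $N = 40$ FM patients and $N = 40$ healthy controls".

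The analysis text in the same section (Data Analyses and Interpretation) reads: "Scores on the depression and trauma history questionnaires will be used as linear regressors to predict ratings of gentle brushing pleasantness".

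The plan does not say:
- whether the powered test is the overall test of the model or a test of particular coefficients;
- whether 0.15 is the effect of the whole model or of each predictor;
- what the third predictor is.

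**The concern.** The hypothesis is about two named predictors. The sample size is the one for rejecting that all three slopes are zero. These are different claims: the overall test can reject because of one predictor only, and if a third predictor is in the model, that one may be neither depression nor trauma. An f² of 0.15 for the whole model also leaves each predictor with a smaller partial effect as soon as more than one contributes.

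This calculation sets the study's N; the 24 and 27 per group derived in the next paragraph are treated as covered by it. A reader will naturally attach the 0.8 to depression and trauma. The risk is in interpretation. A non-significant coefficient could be given more weight as evidence of no association than the design supports, and a significant model could be taken as support for both predictors.

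**Working it through.** **Inputs.** From Section 9: f² = 0.15, three predictors, α = 0.05, target power 0.8, planned N = 80. Assumed here because the plan does not give them: how the effect is split among predictors, and correlations of 0, 0.3 and 0.5 between them.

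**Formula.** Fixed-model regression with p predictors and a test on u of them. Power = P[F′(u, N − p − 1; λ) > F₀.₉₅(u, N − p − 1)], where F′ is noncentral F and λ = f² × N.

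**Step 1: reproduce 77.** With u = 3, p = 3 and f² = 0.15:
- N = 76: power 0.796
- N = 77: λ = 0.15 × 77 = 11.55, df 3 and 73, power 0.802
- N = 80: λ = 12.0, df 3 and 76, power 0.819

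So 77 is the smallest N for the overall test.

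**Step 2: other tests at f² = 0.15 and power 0.8.**
- Two of three predictors jointly (u = 2): N = 68
- Overall test of a model with only two predictors: N = 68
- One coefficient among three (u = 1): N = 55 two-sided, 43 one-sided
- Overall test when each of three uncorrelated predictors has partial f² = 0.15, so whole-model f² = 3 × 0.15 = 0.45: N = 29

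None gives 77. The stated N therefore implies that 0.15 is the whole-model effect, that is R² = 0.15/1.15 = 0.130.

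**Step 3: coefficient power at N = 80 on that reading, uncorrelated predictors.**
- Depression and trauma carry everything equally: partial f² = 0.15/2 = 0.075, λ = 6.0, power 0.68 each. Both significant: about 0.43 (simulation). N for 0.8 per coefficient: 107.
- Three predictors share equally: partial f² = 0.15/3 = 0.05, λ = 4.0, power 0.51 each. Both depression and trauma significant: about 0.25 (simulation). N for 0.8 per coefficient: 159.

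**Step 4: positive correlation ρ (assumed).** With residual variance 1, scale the slopes β so that β′Σβ = 0.15. The partial f² of predictor j is then β_j² / (Σ⁻¹)_jj. For example, take two carriers with ρ = 0.3 and an uncorrelated third predictor. Then β² = 0.15/2.6 = 0.0577, and partial f² = 0.0577 × (1 − 0.09) = 0.0525.

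| Split of the effect | ρ | Third predictor | Partial f² | Power per coefficient |
|---|---|---|---|---|
| Two carriers | 0.3 | uncorrelated | 0.0525 | 0.53 |
| Two carriers | 0.3 | correlated | 0.0497 | 0.50 |
| Two carriers | 0.5 | uncorrelated | 0.0375 | 0.40 |
| Two carriers | 0.5 | correlated | 0.0333 | 0.36 |
| Three equal | 0.3 | uncorrelated | 0.0379 | 0.41 |
| Three equal | 0.3 | correlated | 0.0269 | 0.31 |
| Three equal | 0.5 | uncorrelated | 0.0281 | 0.32 |
| Three equal | 0.5 | correlated | 0.0167 | 0.21 |

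**Step 5: the favourable readings at N = 80.**
- 0.15 is each predictor's partial effect: λ = 12.0, u = 1, power 0.93 per coefficient and about 0.82 for both.
- Joint 2-df test of depression and trauma at partial f² = 0.15: power 0.87. Under an equal three-way split, the joint partial f² is 0.10 with no correlation (power 0.70). With all three correlated at 0.3 or 0.5, power is 0.54 or 0.40.

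**Step 6: partial f² detectable with 80% power at N = 80.** One coefficient: 0.101. Joint 2-df test: 0.125.

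**The case against.** The best defence is that the plan never says 0.15 is a whole-model effect. Read as a partial effect, it gives ample power for each coefficient. The analysis text also names only two regressors. In a two-regressor model the overall test is itself the depression-plus-trauma test, 68 participants suffice at f² = 0.15, and no third predictor could drive the result.

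Part of this stands. A reader might infer that power for depression and trauma is simply far below 0.8. The documents do not support that as a flat statement, because the split, the correlations and the meaning of 0.15 are not given. A reader might also infer that 77 is a miscalculation; it is not, since it reproduces exactly. And the argument that a third predictor could carry the overall test applies only if that predictor is in the fitted model, which the analysis text leaves unclear.

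The rest does not stand. The partial-effect reading does not produce 77: it gives 55 for one coefficient, or 29 for the overall test with three uncorrelated predictors. The two-regressor reading gives 68. The plan's own number points to the overall three-predictor test. Even in the two-regressor model, a significant joint test shows only that at least one of the two matters. Finally, the plan does not state how a null coefficient would be interpreted, so the risk of misreading is a reasonable worry and not a documented intention.

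**Conclusion.** The point holds as a mismatch between the powered test and the stated hypothesis. The sample size is right for the overall 3-df test at whole-model f² = 0.15 (power 0.82 at N = 80), but the 0.8 does not carry over to the individual claims about depression and trauma.

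On the whole-model reading, per-coefficient power is about 0.68 or 0.51 without correlation. With correlations of 0.3 to 0.5 it falls to about 0.53–0.36 with two carriers and 0.41–0.21 with three, depending on whether the third predictor is also correlated. These figures rest on equal splits and assumed correlations. An unequal split could give one predictor adequate power, but at the expense of the other. If 0.15 is a partial effect, there is no shortfall (0.93 per coefficient). The plan should say which it means.

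**What to change.** Keep N = 80 and revise Section 9:

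1. In Sample Size Determination & Power, state that N = 77 and power 0.8 apply to the overall F-test of a three-predictor model with whole-model f² = 0.15.
2. Reconcile the three predictors there with the two regressors in Data Analyses and Interpretation: name the third predictor and add it to the model, or redo the calculation for two.
3. Base any claim about depression or trauma on its own coefficient test. If a joint 2-df test is also used, say that it supports only the claim that at least one of the two matters.
4. Restate power as detectable effects at N = 80: 80% power needs a partial f² of about 0.10 for one coefficient and about 0.125 for the joint 2-df test (both with three predictors in the model).

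The cost is rewording; recruitment and procedures do not change. The downside is that the stated power for individual predictors becomes less favourable.

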
The proposed research is the subject of a pending R00 award and will determine whether light and deep pressure touch have comparable analgesic effects, and whether these effects differ in individuals with chronic pain conditions. It will also determine which factors predict the blunted affective touch perception observed in patients with chronic pain. The central hypothesis is that both light and deep pressure touch exert analgesic benefits, and that these analgesic effects will correlate with the pleasantness of touch. Further, we predict that the analgesic effects of pleasant touch will be reduced in patients with chronic pain, who experience reduced touch pleasantness. This research will advance our understanding of the mechanisms of massage therapy and its effect on those who suffer from chronic pain.

Aim 1 (R00): Determine why individuals with chronic pain show reduced C-LTMR-related touch pleasantness.

Hypotheses: I hypothesize that blunted pleasantness of C-LTMR and deep pressure touch in individuals with chronic pain will be predicted by psychological factors including depression and trauma history (due to the impact of these factors on the μ -opioid system, e.g. [9]).

Aim 2 (R00): Determine whether the analgesic effects of light and deep pressure touch are reduced in individuals with chronic pain, and whether analgesia correlates with pleasantness perception.

Hypotheses: I hypothesize that concurrent or recent administration of light or deep pressure pleasant touch will reduce the perceived pain of a phasic heat stimulus, and that this effect will be reduced in chronic pain patients. Further, I predict that the analgesic effect of affective touch will be correlated with the perceived pleasantness of the touch.

Sub-aim 2b: Determine whether CPM effects of pleasant touch are related to CPM effects of pain.

Hypotheses: I hypothesize that the CPM efficiency for painful and pleasant touch will not be correlated across participants, suggesting divergent mechanisms.

Sub-aim 2c: Determine whether analgesic effects of light stroking or deep pressure are mediated by reductions in respiration rate.

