The proposed research will compare the analgesic effects of light and deep pressure touch to those of neutral touch, determine whether the effects are direct (segmental), and determine whether these effects differ in individuals with chronic pain conditions. It will also determine which factors predict the blunted affective touch perception observed in patients with chronic pain. Finally, it will include continuous respiration monitoring during affective and pain testing to determine whether slower respiration rate underlies (mediates) the analgesic effects of pleasant touch. The central hypothesis is that both light and deep pressure pleasantness are blunted in individuals with chronic pain primarily due to psychological factors, and that the analgesic effects of pleasant touch will also be reduced in patients with chronic pain. Further, we predict that pleasant touch will exert greater (nonsegmental) analgesic benefits than neutral touch, and that this analgesic effect will correlate with the pleasantness of touch. This research will advance our understanding of the mechanisms of massage therapy and its effect on those who suffer from chronic pain.

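### Aim 1 asks why FM patients rate touch as less pleasant than controls, but the stated regression tests only whether depression and trauma scores predict brushing pleasantness, not how much of the FM-control gap they account for

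*Combined protocol and SAP*

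**What the plan says.** Section 6 gives Aim 1 as: "Determine why individuals with chronic pain show reduced C-LTMR-related touch pleasantness". The hypothesis beneath it is that "blunted pleasantness of C-LTMR and deep pressure touch in individuals with chronic pain will be predicted by psychological factors including depression and trauma history". In section 7 the central hypothesis goes further and says that "light and deep pressure pleasantness are blunted in individuals with chronic pain primarily due to psychological factors".

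Section 9, Data Analyses and Interpretation, gives Aim 1 one sentence: "Scores on the depression and trauma history questionnaires will be used as linear regressors to predict ratings of gentle brushing pleasantness". It names no FM-status term, no group-by-score interaction, no mediation analysis and no comparison of the group difference before and after adjustment. It does not say whether patients and controls are pooled. It covers brushing only, although the hypothesis also covers deep pressure.

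Section 9, Sample Size Determination & Power, sizes the study on this regression: "Based on an effect size F^2 of 0.15, three predictors, alpha of 0.05, and power 0.8", from which "this study will require $N = 77$ participants", rounded up to 40 FM and 40 controls. Only two of the three predictors are identified. The same paragraph expects lower pleasantness in FM than in healthy people and says that the sample also suffices for comparisons of pleasant touch, but no model is named for them.

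**The concern.** The aim concerns a difference between two groups and its source. A regression slope says that people with higher depression scores rate brushing lower. The part of a group difference that a factor accounts for is its slope multiplied by how far the groups differ on it. The plan tests the first quantity and never combines it with the second. A factor can therefore predict pleasantness strongly while the groups barely differ on it, and then it accounts for almost none of the gap.

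What is at stake is the Aim 1 conclusion. As written, a positive regression leaves open whether depression or trauma has anything to do with the lower ratings in FM, which is the question that the aim poses.

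**Working it through.** **1. The plan's own figure.** Overall F test, f² = 0.15, three predictors, alpha 0.05, noncentrality 0.15 × N, degrees of freedom (3, N - 4). At N = 77 the noncentrality is 11.55 and power is 0.802; at N = 76 power is 0.796. So 77 reproduces, and N = 80 gives 0.819. Two predictors would need only 68, so the figure does rest on three. It powers a test that R² differs from zero.

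**2. Planned test against share of the gap.** Assumed, because the documents give no values: FM-control gap 0.8 within-group SD; within-group depression slope -0.35 SD per SD; trauma correlated 0.3 with depression, with no slope of its own; 40 + 40 participants. Let δ be the FM excess in depression, in SD. The share explained is 0.35 × δ / 0.8.

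| δ | Share of gap explained | Depression significant, two scores, pooled | Same, FM status added |
|---|---|---|---|
| 0 | 0 / 0.8 = 0% | about 79% | 84-87% |
| 0.25 | 0.0875 / 0.8 = 11% | about 92% | 84-87% |
| 0.5 | 0.175 / 0.8 = 22% | about 96% | 84-87% |
| 1.0 | 0.35 / 0.8 = 44% | about 99% | 84-87% |

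Repeat runs differ by one or two points (79-81% in the first row). The 79% is power to detect a slope that truly exists; it is not a type I error for the prediction hypothesis. The table shows only that the test result does not track the share.

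**3. A second set of assumptions.** Each score has slope √(0.15 / (2 + 2 × 0.3)) = 0.24, so that f² = 0.15 within groups; 2,000 runs per scenario.
- *Scores predict, group means equal (0% explained; gap 0.5-0.9 SD).* The two-score regression is significant in 78-84% of runs, and a test of the total indirect effect (group to scores to pleasantness) in about 3%.
- *Scores higher in FM (depression by 0.5-1.2 SD, trauma by half that), no within-group slope (0% explained; gap 0.5-1.0 SD).* The two-score regression is significant in 8-44% of runs, and the indirect-effect test in about 1-5%.
- *Scores explain part of the gap (direct gap 0.3 SD; depression higher by 0.5, 0.8 or 1.0 SD, trauma by half that).* The indirect-effect test has about 36%, 64% and 76% power at N = 80.

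**4. Precision.** In the δ = 1.0 case of step 2, the explained part averages 0.35 SD, with a 95% range over simulated trials of about 0.11 to 0.64 SD.

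**The case against.** The strongest defence is that the regression matches the hypothesis as written. Section 6 says that blunting will be predicted by these factors, section 9 repeats this, and sections 6 and 7 both describe the task as finding which factors predict blunted touch. That stands: a reader might infer that the regression is wrong for its hypothesis, and the documents do not support that. The mismatch is with the question in the aim's title and with one clause in section 7.

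The unnamed third predictor may be FM status. If so, the model already contains the adjusted group coefficient. Testing the scores with FM status in the model also removes the spurious positives of the second scenario in step 3 (joint test of the scores about 5%). It does not make the score test track the share (84-87% throughout step 2). The overall three-predictor F test, which is the one powered, is significant in 42-97% of runs in that second scenario through FM status alone.

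Three stronger readings also fail:
- *The plan has no FM-control comparison of pleasantness.* The sample-size text implies one; what is missing is its model and its link to the regression.
- *The section 7 wording commits the sponsor to more than half of the gap.* It appears once, in Background, with no threshold.
- *A significant slope will be reported as the reason for blunting.* Nothing in the documents says so.

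Finally, the suggested addition is cross-sectional and cannot establish cause either. That is correct and limits what it may claim.

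**Conclusion.** The concern holds in limited form. The planned analysis can answer whether depression and trauma predict brushing pleasantness. It cannot say how much of the FM-control gap they account for, which is what the aim and section 7 ask. Under the assumed inputs, depression is significant in about 79% of trials when it explains none of the gap. It is significant in about 99% when it explains 44%.

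These percentages rest on the assumed gap, slope, correlation and group differences. That a slope alone is not a share of a gap does not. The sample-size figure is correct for the test that it describes. This is a cheap improvement to the analysis and its wording, not a flaw that invalidates the study.

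**What to change.** In section 9, Sample Size Determination & Power and Data Analyses and Interpretation:

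1. Keep the regression as the powered prediction test. Name the third predictor and state that FM and control participants are pooled. (Restricted to 40 FM patients, power would be about 0.47 with three predictors and 0.55 with two.)
2. Add the FM-control difference in brushing pleasantness from a model with group alone, then with group, HADS depression and CTQ. Report the change in the group coefficient, in total and per predictor (slope × group difference on that score), with a bootstrap 95% CI, as an estimate.
3. Say that a factor accounts for part of the gap only if its CI excludes 0; otherwise limit the conclusion to prediction.
4. In section 7, drop or soften the clause attributing the blunting mainly to psychological factors. A rule requiring the lower limit to exceed half of the gap is not advised: in two simulations it was met in only about 9% and 15% of trials at a true share of 69%.
5. State that N = 77 does not power the indirect effect (about 36% at a 0.5 SD depression difference under the step 3 assumptions) and that cross-sectional data do not support a causal reading.

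The cost is one extra model, a bootstrap and revised wording, on data already collected. The price is a wide interval and a more modest conclusion.

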6. SPECIFIC AIMS

Light stroking and deep pressure touch are engaged by many complementary health practices, most notably massage therapy. Massage therapy uses touch in a therapeutic context to achieve significant reductions in stress, pain, and depression [1]. There is little understanding, however, of the mechanisms by which specific touch components- such as light stroking and deep pressure- exert affective and analgesic benefits. The pleasantness of light stroking touch has been linked to the activation of C low-threshold mechanoreceptor (C-LTMR) fibers, unmyelinated sensory fibers that respond to slow gentle stroking of the skin and project to opioidergic brain regions including the insula and cingulate cortex. How C-LTMR stimulation gives rise to pleasant sensation is unknown, though studies of monkeys (e.g. [2]) and preliminary data from humans [3] suggest that opioids play a role. The affective sensory pathways of deep pressure touch, in contrast, are less studied. Numerous clinical studies have found that deep pressure touch is calming and is superior to light touch in massage therapy [4, 5]. In addition, analgesic benefits of both light touch and deep pressure have been demonstrated in the laboratory [6, 7]. However, there is a significant gap in our knowledge of how these pathways differ in individuals with chronic pain, and whether pleasant touch has the same level of analgesic effect. In our previous work, chronic pain patients showed reduced perception of C-LTMR-optimal touch: in striking contrast to healthy volunteers, pain patients rated slow and fast brushing as equivalent in both intensity and pleasantness [3]. This has now also been shown in patients with low back pain [8]. In addition, individuals with chronic pain show reduced ability to downregulate their pain experience through competing sensations, as demonstrated in the Conditioned Pain Modulation (CPM) paradigm. Furthermore, an emerging body of research suggests that breathing slower during nociceptive stimulation is associated with reduced pain perception [32-36]. Reduced respiration rate has been shown to support the pain-relieving effects of some mind-body therapies, including meditation [37, 38]. Although there is some evidence that pleasant touch reduces respiration rate (in infants) [39], it is currently unknown whether touch-induced reductions in respiration rate mediate the pain-relieving effects of C-LTMR optimal touch. In sum, we do not know how processing of affective touch and its analgesic benefits may differ in people with chronic pain, who frequently utilize touch-based therapies in an effort to relieve their pain. The long-term goal of this research is to elucidate the sensory-affective mechanisms of light and deep touch in health and in chronic pain, in order to advance understanding of manual therapies and their effects on pain and psychological well-being.

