We will then familiarize participants with our touch tasks and collect baseline ratings. A brief training will be conducted to introduce sensations and rating scales. We will then collect several rounds of ratings of approximately 1 min each of light gentle brushing (using a soft paint brush), deep pressure (using a lymphedema compression sleeve inflated to <100mmHg or a commercially available massager), a neutral touch (tapping), and heat pain using a Medoc or Thermal QST thermode. Testing will occur on the limbs in areas identified as most comfortable by patients. Participants will be asked to rate their mood at various timepoints throughout the study.

Finally, we will conduct a classic CPM paradigm with a cold water bath where participants immerse their forearm into a 12°C refrigerated circulating water bath (e.g. NESLAB Digital One RTE 7, Thermo Scientific, Newington, NH, USA) for 60 seconds. The CPM paradigm is used to test the analgesic effects of a concurrent or recent test pain stimulus on a conditioned pain stimulus. The effects of the cold-CPM paradigm will be contrasted with a modified affective-CPM paradigm in Session 2. The cold-CPM block will include: phasic heat pain (baseline), heat pain while concurrently placing hand in the cold water bath (test), and then test phasic heat perception once again (post-test), as follows:

Calibration (psychophysical testing): determine level of heat to administer that results in a verbal pain rating of 6 out of 10 (0 = no pain; 10 = intolerable pain). An ascending series of 10s-duration heat stimuli between 39 and 50C will be administered until a stimulus is rated as a 6 out of 10. If a 6 is surpassed, stimuli will be decreased in .5C increments until the rating of 6 is achieved. Ratings will be confirmed by administering a 30s stimulus and adjusted if necessary.

Baseline: Heat will be administered using a thermode for 30s. Pain intensity ratings for the heat will be collected every 10s for a total of 3 ratings.

Test: 0-30s: rate unpleasantness and intensity of the cold water stimulus. 30-60s: administer heat pain using a thermode concurrently; pain intensity rating of heat pain given every 10sec for a total of 3 ratings

Post-test: Repeat of baseline.

Session 1 will occur at the ACTRI and will take approximately 1 hour to complete.

Session 2: Affective-CPM Paradigm

A urine pregnancy (if applicable) and opiate test will be performed.

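### Aim 1 regresses the raw brushing pleasantness rating with no neutral-touch comparator, so blunted C-LTMR-related pleasantness cannot be told apart from lower ratings of all touch

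*Combined protocol and SAP*

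**What the plan says.** Section 6 states Aim 1 as: "Determine why individuals with chronic pain show reduced C-LTMR-related touch pleasantness". The sample-size text in Section 9 gives the expected finding: "current depression and trauma history will be significant predictors of blunted C-LTMR touch pleasantness". The whole analysis is one sentence under Data Analyses and Interpretation: the depression and trauma questionnaire scores enter a linear regression to "predict ratings of gentle brushing pleasantness". It names no tapping term, no contrast between touch types and no group term.

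The sample size rests on this regression: "Based on an effect size F^2 of 0.15, three predictors, alpha of 0.05, and power 0.8, this study will require" 77 participants, rounded up to 80, to "include $N = 40$ FM patients and $N = 40$ healthy controls". Three predictors are counted, but only two are named.

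The comparator data exist. Session 1 collects several rounds of ratings of brushing, pressure, tapping and heat. Outcome Measure(s) says that pleasantness is rated for each stimulus at the Session 1 baseline. Tapping pleasantness is rated again in the Session 2 blocks. The planned ANOVA compares touch types only on the change in pain. The sample-size text mentions comparisons of pleasant touch but gives no model for them.

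**The concern.** The outcome measures how pleasant brushing is. The conclusion concerns a kind of touch, C-LTMR-related touch, with a mu-opioid rationale in Section 6. If depression or trauma history lowers every pleasantness rating, through anhedonia or scale use, brushing ratings fall as well. The coefficient can then be significant although nothing particular to affective touch is affected.

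Part of the earlier evidence cited in Section 6 was a comparison between stimuli within person: "pain patients rated slow and fast brushing as equivalent in both intensity and pleasantness". An absolute brushing rating does not carry such a comparison. Fast brushing is not described in this study, so tapping is the only neutral touch that could supply one. Aim 2 already uses neutral touch as its reference; Aim 1 does not.

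At stake is the interpretation of Aim 1. A significant coefficient would be read as explaining blunted C-LTMR pleasantness when the data cannot distinguish that from a general effect on touch ratings.

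**Working it through.** **1. The plan's own figure.** Overall F test of a regression with u = 3, v = N - 4 and noncentrality f² × N.
- N = 77: 0.15 × 77 = 11.55, power 0.802.
- N = 80: 0.15 × 80 = 12.0, power 0.819.

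So 77 reproduces. An overall test with two predictors would need 68, and a test of one predictor out of three would need 55. The sample size is right for its inputs; the issue is the outcome variable.

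**2. What the model estimates.** Write brushing = G + S_b and tapping = G + S_t, where G is a person's general tendency to rate touch as pleasant. Regressing brushing on depression estimates (effect on G) + (effect on S_b). Aim 1's wording concerns the second term; the model returns the sum. Regressing brushing minus tapping cancels G and leaves (effect on S_b) - (effect on S_t).

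**3. Size for the planned model.** Assumptions, none from the documents: each score correlates r = -0.30 with brushing and equally with tapping; the scores correlate ρ = 0.3 or 0.5; there is no brushing-specific effect. N = 80 is from the plan. The sign of r does not affect the results below.

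Overall test: R² = 2r²/(1 + ρ), f² = R²/(1 - R²), with 2 and 77 df.
- ρ = 0.3: R² = 0.18/1.3 = 0.138, f² = 0.161, noncentrality 12.9, power about 0.89.
- ρ = 0.5: R² = 0.18/1.5 = 0.120, f² = 0.136, noncentrality 10.9, power about 0.83.

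These f² values lie on either side of the plan's 0.15.

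Depression coefficient: partial r = r(1 - ρ)/√[(1 - r²)(1 - ρ²)].
- ρ = 0.3: 0.21/0.91 = 0.231, power about 0.55.
- ρ = 0.5: 0.15/0.826 = 0.182, power about 0.37.

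The formula treats the scores as fixed. Simulation with randomly drawn scores gives slightly lower values: about 81-88% overall and about 36-53% for depression.

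**4. Size for the contrast.** On the standardised scale, the covariance of depression with brushing minus tapping is -0.30 - (-0.30) = 0. In simulation the depression coefficient is significant in about 5% of trials in every setting tried.

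A second simulation (4,000 runs per setting, both scores acting only on G, ρ = 0.3) gives the same picture for the joint test of both scores:

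| Raw f² | Raw brushing | Brushing minus tapping |
|---|---|---|
| 0.05 | 37-40% | about 5% |
| 0.15 | 85-86% | about 5% |
| 0.25 | 97-98% | about 5% |

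**5. Tapping as a covariate instead.** With one predictor, partial r = r(1 - r_bt)/√[(1 - r²)(1 - r_bt²)], where r_bt is the brushing-tapping correlation. For r_bt = 0.5, 0.7 and 0.8 this is 0.182, 0.132 and 0.105, and the test is significant in 37%, 22% and 15% of trials. With both scores at f² = 0.15, the rate runs from 22% (G is 70% of rating variance) to 62% (G is 30%). Tapping measures G with error, so part of the general effect stays in the coefficient.

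**6. Sample size after the change.** With the difference as outcome, three predictors and f² = 0.15, required N is again 77, with power 0.819 at 80. The documents give no effect size for the difference, so f² = 0.15 is an assumption there.

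**The case against.** **The protocol does not claim exclusivity.** A reader might infer that the plan will report blunting specific to C-LTMR touch. The documents do not support this. Aim 1 speaks of C-LTMR-related pleasantness, and both its hypothesis and Section 7 also predict blunting for deep pressure. This stands. The point is that an effect equally present for neutral tapping would not support a C-LTMR or affective-touch explanation.

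**An absolute level is a legitimate target.** Section 7 and the sample-size text describe reduced pleasantness of stroking touch as a level, and the planned outcome measures that. The regression validly tests whether the scores predict brushing pleasantness. This also stands, and is why the planned model should stay.

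**A general effect may be the hypothesised route.** If depression and trauma act through the mu-opioid system, they could lower all pleasantness, and removing the tapping component would discard part of the effect. This is fair. The contrast answers a narrower question and belongs beside the planned model, as a secondary test.

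**The inputs are assumed.** Equal correlations with brushing and tapping have no support in the documents. Neutral touch scored on a scale whose minimum is no pleasantness may sit near the floor. If depression correlated -0.30 with brushing but only -0.15 with tapping for that reason, the contrast would no longer be null. Hence the floor check.

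**A rate of about 79% may be tempting.** It is the power of a single predictor at r = 0.30 with N = 80. The plan enters two scores and counts an unnamed third predictor, so 79% does not describe the planned model. If the third predictor is group, all the figures above change. Nothing indicates that it is tapping.

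**Conclusion.** The point holds in a limited form. Aim 1 has no neutral-touch comparator, so a lower general rating of touch and blunted C-LTMR-related or affective pleasantness give the same result in the planned model. This follows from the model and needs no assumed figures.

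The size is illustrative. Under a purely general effect with the stated correlations, the planned two-score model is significant overall in about 81-88% of trials, against about 5% for the depression coefficient on the contrast. The 81-88% is not a type I error rate of the planned test, because the association with brushing is real in that scenario. It is how often a general effect would be open to misattribution.

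A reader might go further and conclude that the regression is invalid, that N = 80 is wrong, or that adjusting for tapping would settle the matter. The regression answers its own narrower question, 77 reproduces exactly, and covariate adjustment leaves rates of 15-62% under the assumptions above. The change is worth making before analysis, but it does not undermine the study.

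**What to change.** Keep the planned regression. Add to Data Analyses and Interpretation:

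- A prespecified secondary test of the depression and trauma scores on the Session 1 difference, brushing minus tapping pleasantness, with each rating averaged over its repeated rounds. With two touch types per person this is equivalent to a touch-type-by-predictor interaction.
- An interpretation rule. Attribute an effect to C-LTMR or affective touch only if this test supports it. Otherwise report that depression or trauma predicts lower brushing pleasantness, without claiming that this differs from neutral touch.
- A check of the tapping distribution for a floor. Tapping ratings that cannot fall further could make a general effect look particular to brushing.
- If wanted, a model with tapping as covariate, labelled as supportive only.
- The name of the third predictor counted in the sample size.

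The cost is a few sentences in the plan; no new data, visits or participants are needed. The downside is power: a difference of two ratings is less reliable than either rating, so a non-significant contrast does not show that the effect is general, and the report should say so.
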